4.3 Exclusion Criteria

Patients will be excluded from enrollment in study LA38-EXT if they meet **any** of the following criteria:

- 1. Plan to participate in another clinical trial at any time from the day of enrollment until 30 days post-treatment in the current study
- 2. For only those patients who were treated with deferoxamine in study LA38-0411 (Group 2): Presence of any medical condition (including clinically significant laboratory abnormalities, such as ALT ≥ 5 x ULN or creatinine ≥ 2 x ULN), psychological condition, or psychiatric condition which in the opinion of the investigator would cause participation in the study to be unwise.

- 3. Pregnant, breastfeeding, or planning to become pregnant during the study period.
- 4. Treatment failure after 1 year on deferiprone which in the investigator's judgment indicates the need for the patient to be started on a different iron chelator

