4.5.3 Treatment Interruptions

Study medication will be interrupted for ANY of the following reasons:

Infection, fever, or decrease in ANC:

- If the patient develops an infection during the study, deferiprone must be interrupted immediately and neutrophil count should be obtained and monitored more frequently (every 2 days if ANC <1.5 x 10⁹/L). Patients should be advised to report immediately to their physician any symptoms indicative of infection such as fever, sore throat, and flu-like symptoms. They will be provided with a thermometer, and instructed to seek immediate medical attention at a hospital or clinic if they experience fever (temperature >38.0° C/100.4°F). Body temperature may be measured at the mouth, axilla, or ear. Patients/legal guardians will be provided with an emergency services card with contact information, and will be advised to carry this card at all times. In presence of confirmed fever and/or infection, they will be required to have their neutrophil counts tested as soon as possible and no later than 24 hours after the symptoms of infection are detected. Therapy with deferiprone can be re-initiated once all symptoms have been resolved and it is deemed safe by the investigator.
- If temperature is >38.0°C/100.4°F and ANC is \le 0.5 x 10⁹/L, the following must be done:
 - Commence therapy with antibiotics immediately (treatment should depend on the site of the suspected infection and on local antibiotic policy)
 - Perform a chest x-ray, and collect blood and other relevant cultures (if possible, collect culture samples before initiating antibiotics)

• If the patient develops moderate neutropenia while on deferiprone, therapy must be interrupted immediately and neutrophil count must be obtained and monitored every 2 days. Therapy with deferiprone can be re-initiated once two successive ANCs are >1.5 x 10⁹/L and it is deemed safe by the investigator. The patient will be withdrawn from the study if the ANC remains <1.5 x 10⁹/L by the end of a 2-week period (14 days).

For definitions of and further detail on the management of neutropenia, see Section 7.2.1.8.1.

Increase in ALT:

If a patient whose ALT level was normal at baseline is confirmed to have serum ALT levels $\geq 5 \text{ x ULN}$ on 2 consecutive assessments, deferiprone treatment may be interrupted based on investigator judgment.

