5.2.3 Adverse Events of Special Interest

5.2.3.1 Neutropenia

Patients taking deferiprone were monitored for neutropenia, defined as a confirmed absolute neutrophil count (ANC) less than $1.5 \times 10^9/L$. Categories of neutropenia are as follows:

- Mild: A confirmed ANC $< 1.5 \times 10^9/L$ but $\geq 1.0 \times 10^9/L$
- Moderate: A confirmed ANC $< 1.0 \times 10^9/L$ but $\geq 0.5 \times 10^9/L$
- Severe: A confirmed ANC $< 0.5 \times 10^9/L$. Severe neutropenia is also referred to as agranulocytosis.

For a case of neutropenia to be confirmed, there must be 2 consecutive counts, a maximum of 3 days apart, that are both less than the specified value. If both counts are below $1.5 \times 10^9/L$ but are not in the same severity category, a third count was required to determine the severity.

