6.3.4 Analysis of Safety

The incidences of AEs and SAEs reported from the start of deferiprone therapy for all patients will be tabulated. For patients continuing on deferiprone, this time period will be from the start of LA38-0411 to the completion of LA38-EXT; for those switching to deferiprone, it will be from the start of LA38-EXT to the completion of LA38-EXT. AEs will be summarized by worst severity and by relationship to the study medication. Time to onset and duration of all SAEs, of AEs of special interest such as neutropenia, agranulocytosis, increased ALT, and arthralgia: 1) the mean time to the first onset and the mean time to the last recurrence will be calculated, and 2) the mean duration for the first episode and the mean duration for any recurrent episodes, excluding the first episode, will be calculated for all SAEs and AEs of special interest.

The percentage of discontinuations due to AEs will be calculated, and the AEs leading to discontinuation will be summarized in a frequency table.

Laboratory data (hematology and chemistry) will be summarized using descriptive statistics for continuous variables and frequency tables for discrete variables. The incidences of out-of-range data will be tabulated, and the changes from baseline to the end of study will be presented in shift tables.

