14.3 Safety Analyses

14.3.1 Adverse Events

Table 14.3.1.1 Overall summary of adverse events – Safety population

Table 14.3.1.2 Summary of adverse events – Safety population

Table 14.3.1.3 Summary of most common adverse events ($\geq 5\%$ in total) – Safety population

Table 14.3.1.4 Summary of adverse drug reactions – Safety population

Table 14.3.1.5 Summary of most common adverse drug reactions ($\geq 5\%$ in total) – Safety population

Table 14.3.1.6 Summary of serious adverse events – Safety population

Table 14.3.1.7 Summary of serious adverse drug reactions – Safety population

Table 14.3.1.8 Summary of adverse events by causality – Safety population

Table 14.3.1.9 Time to the first onset of SAEs – Safety population

Table 14.3.1.10 Time to the first onset of AEs of special interest such as neutropenia, agranulocytosis, increased ALT, arthralgia – Safety population

Table 14.3.1.11 Time to the last recurrence of SAEs – Safety population

Table 14.3.1.12 Time to the last recurrence of AEs of special interest such as neutropenia, agranulocytosis, increased ALT, arthralgia – Safety population

Table 14.3.1.13 Duration of the first onset of SAEs – Safety population

Table 14.3.1.14 Duration of the first onset of AEs of special interest such as neutropenia, agranulocytosis, increased ALT, arthralgia – Safety population

Table 14.3.1.15 Duration of the last recurrence of SAEs – Safety population

Table 14.3.1.16 Duration of the last recurrence of AEs of special interest such as neutropenia, agranulocytosis, increased ALT, arthralgia – Safety population

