Note: Similar tables will be produced for GGT, lactate dehydrogenase (LDH), sodium, potassium, chloride, glucose (fasting at screening visit only), total, direct and indirect bilirubin, AST, ALT, albumin; blood urea nitrogen, calcium, creatinine, uric acid, alkaline phosphatase, and amylase.
Data source: 16.2.12 Listing of chemistry

Table 14.3.6.2.3 Shift table for total protein in abnormal range at baseline vs last assessment:
DFP+DFP group

		Last Assessment				
		n (%)	Low	Normal	High	P-value (McNemar's test)
Baseline	Low	xx (xx)	xx (xx)	xx (xx)	0xxxx	
	Normal	xx (xx)	xx (xx)	xx (xx)		
	High	xx (xx)	xx (xx)	xx (xx)		

Note: Similar tables will be produced for GGT, lactate dehydrogenase (LDH), sodium, potassium, chloride, glucose (fasting at screening visit only), total, direct and indirect bilirubin, AST, ALT, albumin; blood urea nitrogen, calcium, creatinine, uric acid, alkaline phosphatase, and amylase.
Data source: 16.2.12 Listing of chemistry

Table 14.3.6.2.4 Shift table for total protein in abnormal range at baseline vs last assessment: DFO+DFP group

		Last Assessment				
		n (%)	Low	Normal	High	P-value (McNemar's test)
Baseline	Low	xx (xx)	xx (xx)	xx (xx)	0xxxx	
	Normal	xx (xx)	xx (xx)	xx (xx)		
	High	xx (xx)	xx (xx)	xx (xx)		

Note: Similar tables will be produced for GGT, lactate dehydrogenase (LDH), sodium, potassium, chloride, glucose (fasting at screening visit only), total, direct and indirect bilirubin, AST, ALT, albumin; blood urea nitrogen, calcium, creatinine, uric acid, alkaline phosphatase, and amylase.
Data source: 16.2.12 Listing of chemistry

Table 14.3.6.3.1 HIV Antibody at each assessment

	Treatment				P-value (Fisher's exact test)
	DFP+DFP		DFO+DFP		
	N	Positive n (%)	N	Positive n (%)	
Baseline	xxx	xx (xx)	xxx	xx (xx)	0xxxx
Month 6	xxx	xx (xx)	xxx	xx (xx)	0.xxxx
Year 1	xxx	xx (xx)	xxx	xx (xx)	0.xxxx
Year 3	xxx	xx (xx)	xxx	xx (xx)	0.xxxx

Note: Similar tables will be produced for Hepatitis B and C.

Data source: 16.2.13 Listing of serology

Table 14.3.7.1 Female patients with positive pregnancy test during the study

	Treatment	
	DFP+DFP	DFO+DFP
Pregnancy test: Positive		
Patient ID	XXXXXX XXXXXX XXXXXX XXXXXX	XXXXXX XXXXXX XXXXXX XXXXXX

Data source: 16.2.14 Listing of pregnancy

Table 14.4.1 The number and percent of patients who had compliance $\leq 80\%$ or $\geq 120\%$ during the study

	Treatment				P-value (Fisher's exact test)
	DFP+DFP		DFO+DFP		
Compliance	N	Percent	N	Percent	
< 80%	xx	xx.x%	xx	xx.x%	0xxxx

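### The ALT shift table uses only the last value and one ungraded High category, so no planned summary counts patients whose ALT reached 5 x ULN, although increased ALT is an event of special interest.

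*SAP*

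**What the plan says.** SAP 6.3.4 gives onset, recurrence and duration analyses to "AEs of special interest such as neutropenia, agranulocytosis, increased ALT, and arthralgia", and the table list in SAP 14.3.1 repeats the term: "Time to the first onset of AEs of special interest such as neutropenia, agranulocytosis, increased ALT, arthralgia". Neither place gives a cut-off, a confirmation rule or a list of coded terms for increased ALT. Neutropenia is treated differently. SAP 5.2.3.1 says "Patients taking deferiprone were monitored for neutropenia, defined as a confirmed absolute neutrophil count (ANC) less than" 1.5 x 10^9/L, with three severity bands and a two-count confirmation rule.

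The planned biochemistry displays are shown for total protein, and notes in SAP 14.3.6.2, the figure list and SAP 17 extend them to ALT and AST. They are:

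- values by visit, and change from baseline by visit, each with N, mean, SD, minimum and maximum (Tables 14.3.6.2.1 and 14.3.6.2.2);
- a three-by-three Low/Normal/High table for each group, titled "Shift table for total protein in abnormal range at baseline vs last assessment" (Tables 14.3.6.2.3 and 14.3.6.2.4);
- figures of the mean and of the proportion abnormal at each assessment.

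The protocol uses 5 x ULN in two places. Section 4.3 gives it as an example within an investigator-judgement exclusion that applies to Group 2 only: "such as ALT ≥ 5 x ULN or creatinine ≥ 2 x ULN". Section 4.5.3 reads "If a patient whose ALT level was normal at baseline is confirmed to have serum ALT levels" at or above 5 x ULN "on 2 consecutive assessments, deferiprone treatment may be interrupted based on investigator judgment". No table, figure or text in the SAP refers to 5 x ULN or to any other multiple of ULN.

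**The concern.** A shift table is the usual place to look for laboratory worsening in a long-term safety report. This one keeps a single post-baseline value per patient and does not grade how high that value is. For ALT, the clinically interesting information is the peak and its size relative to ULN, and both are lost.

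The loss matters most for patients who enter with raised ALT. Section 4.5.3 refers specifically to patients with normal ALT at baseline, so the protocol allows that others are not normal. Those patients start in the High row and have no worse category to move to.

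At stake is whether the clinical study report can answer a simple question about a known reaction to the drug: how many patients in each group reached the ALT level that the protocol itself singles out.

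**Working it through.** The plan states no figure for this point, so there is nothing of that kind to reproduce. The check has three steps.

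**1. What each kind of patient contributes to the shift table.** These are hypothetical patients, using the shell for Tables 14.3.6.2.3 and 14.3.6.2.4.

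| Baseline ALT | Worst post-baseline | Last assessment | Cell in the shift table |
|---|---|---|---|
| Normal | 12 x ULN | Normal | Normal to Normal |
| Normal | 1.1 x ULN | 1.1 x ULN | Normal to High |
| Normal | 12 x ULN | 12 x ULN | Normal to High |
| 1.1 x ULN | 12 x ULN | 12 x ULN | High to High |

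The first row shows no change. The second and third cannot be told apart. The fourth looks stable.

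**2. How much of the data the shift table uses.** Extension biochemistry is taken at Visits 1, 3, 5, 7 and 9 (Protocol 7.2.2). If Group 2's baseline is Week 0 of the extension, the scheduled post-baseline values are at Weeks 26, 52, 78 and 104, which makes 4. For Group 1, counted from the parent-study baseline, the shell for Table 14.3.6.2.1 lists Months 1 to 12, 18, 24, 30 and 36: 12 + 4 = 16. The shift table uses 1 of 4 and 1 of 16 respectively.

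**3. Scale.** Protocol 1.3 reports increased ALT as an adverse reaction in 54 of 712 patients: 54/712 = 7.58%, which matches the printed 7.6%. The parent study plans 300 patients and only its completers may enter, so 300 is an upper bound. Taking 60% to 100% of it as an assumption gives 180 to 300 treated patients:

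- 180 x 54/712 = 13.7, about 14 patients;
- 300 x 54/712 = 22.8, about 23 patients.

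That rate covers reported increases of any size judged at least possibly related. It is not a rate for 5 x ULN, which the documents do not give. For an assumed true rate p in n patients, the expected count is n x p and the chance of at least one case is 1 - (1 - p)^n:

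| n | p | Expected patients | Chance of at least one |
|---|---|---|---|
| 180 | 0.5% | 0.9 | 59% |
| 180 | 3% | 5.4 | over 99% |
| 300 | 0.5% | 1.5 | 78% |
| 300 | 3% | 9.0 | over 99% |

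Over this range the count is small, but it is more likely than not to be above zero.

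**Persistence.** Protocol 9.4.1.4 would tabulate out-of-range laboratory values seen on two consecutive measures. SAP 6.3.4 tabulates out-of-range values without that condition. The SAP text therefore no longer provides for a summary of sustained abnormality either.

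**The case against.** The strongest reply is that severe elevations will not be hidden. Tables 14.3.6.2.1 and 14.3.6.2.2 give the maximum value and the maximum change at each visit, so a patient with a raised baseline who climbs to 12 x ULN would appear there. Listing 16.2.12 carries every central chemistry result. Protocol 7.2.2 requires a clinically significant abnormality that is not part of a condition already recorded to be reported as an adverse event. Such events enter the incidence, causality, onset and duration tables.

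All of this stands, and it rules out a stronger reading. A reader might infer that ALT at or above 5 x ULN would never be seen, or that the outputs could show no worsening at all. The documents do not support that; the blind spot belongs to the shift table and to the absence of a patient count. A maximum is one patient per visit and does not say how many others were close to it. A listing is not a summary. The adverse-event route depends on investigator judgement. SAP 6.3.4 promises a worst-severity summary, but the table list has none by term, only one overall row for severe events in Table 14.3.1.1.

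A reader might also take 5 x ULN for a stopping limit. It is an example exclusion for one group and a discretionary trigger for patients with normal baseline ALT. Using it for patients with raised baseline ALT is a reporting choice, not an extension of the rule.

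Finally, it may be tempting to derive ALT onset and duration from the laboratory values. With extension samples about 26 weeks apart, that would be coarser than the adverse-event start and stop dates defined in SAP 6.1.1.

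**Conclusion.** The concern holds as a gap in the planned summaries. For an event of special interest in a study whose primary objective is safety, the ALT shift table discards resolved peaks, does not grade the High category, and cannot show worsening from a High baseline. No other planned summary counts patients at or above 5 x ULN. This follows from the table shells alone and needs no assumption about how many patients start above ULN, a share the documents do not give.

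The size is modest: an uncounted group of perhaps 0.9 to 9 expected patients, under assumed rates of 0.5% to 3% and an assumed 180 to 300 treated. The missing wording for increased ALT would, by itself, be only missing detail. The change should be made because it is cheap and bears on the primary objective.

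**What to change.** In SAP 14.3.6.2, add one table for ALT and one for AST, by group, of the worst post-baseline value in multiples of ULN:

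- use all post-baseline assessments, not only the last;
- include a category at or above 5 x ULN; further bands such as 3 x and 10 x ULN are a reviewer's choice and do not come from the documents;
- split by baseline status, normal or raised;
- add the number of patients with two consecutive values at or above 5 x ULN, with a footnote that scheduled extension samples are about 26 weeks apart, so shorter episodes can be missed.

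Keep the onset and duration tables based on recorded adverse events as primary. If a laboratory-derived onset is also shown, label it as first observed.

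The cost is SAP wording and a small amount of programming on values already collected. The limitation is coarse timing from semi-annual sampling. No visit, sample or clinical rule changes.

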14.3.2 Vital Signs

Table 14.3.2.1 Temperature at each assessment – Safety population

Table 14.3.2.2 Change in temperature from baseline to each follow-up assessment – Safety population

Note: Similar tables will be produced for resting heart rate, respiration, systolic blood pressure, and diastolic blood pressure.

14.3.3 Weight and Height

Table 14.3.3.1 Weight at each assessment – Safety population

Table 14.3.3.2 Change in weight from baseline to last assessment – Safety population

Table 14.3.3.1 Height at each assessment – Safety population

Table 14.3.3.2 Change in height from baseline to last assessment – Safety population

14.3.4 Concomitant Medications

Table 14.3.4.1 Concomitant medications – Safety population

14.3.5 12-Lead ECG

Table 14.3.5.1 Heart rate of 12-Lead ECG at each assessment – Safety population

Table 14.3.5.2 Change in heart rate of 12-Lead ECG from baseline to each follow-up assessment – Safety population

Note: Similar tables will be produced for PR, QRS, QT, QTcF, and QTcB.

Table 14.3.5.3 Shift table for clinically significant abnormality for 12-Lead ECG – Safety population

14.3.6 Laboratory Data

14.3.6.1 Hematology

Table 14.3.6.1.1 Hemoglobin at each assessment – Safety population

Table 14.3.6.1.2 Change in hemoglobin from baseline to each follow-up assessment – Safety population

Table 14.3.6.1.3 Shift table for hemoglobin in abnormal range at baseline vs. last assessment – Safety population

Note: Similar tables will be produced for total white blood cell (WBC), absolute neutrophil count (ANC), and platelets.

14.3.6.2 Biochemistry

Table 14.3.6.2.1 Total protein at each assessment – Safety population

Table 14.3.6.2.2 Change in total protein from baseline to each follow-up assessment – Safety population

Table 14.3.6.2.3 Shift table for total protein in abnormal range at baseline vs. last assessment – Safety population

Note: Similar tables will be produced for GGT, lactate dehydrogenase (LDH), sodium, potassium, chloride, glucose (fasting at screening visit only), total, direct and indirect bilirubin, AST, ALT, albumin; blood urea nitrogen, calcium, creatinine, uric acid, alkaline phosphatase, and amylase.

14.3.6.3 Serology

Table 14.3.6.3.1 HIV at each assessment – Safety population

Note: Similar tables will be produced for Hepatitis B and C. – Safety population

14.3.7 Pregnancy test

Table 14.3.7.1 Female patients with positive pregnancy test during the study – Safety population

14.4 Treatment compliance

14.4.1 The number and percent of patients who had compliance <80% or >120% during the study – Safety population

14.5 Transfusion information

Table 14.5.1 Overall mean of transfusional iron input (mg/kg/day) during the study – Safety population

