3.3 Rationale for Selection of Doses

The dosage of deferiprone for each patient will be between 25 and 33 mg/kg t.i.d., for a total daily dose of 75 to 99 mg/kg. This is the approved therapeutic dose range, and the same as

that being used in study LA38-0411.

Dosing will be as follows:

- Patients who were treated with deferiprone in LA38-0411 will continue on the same dosing regimen in LA38-EXT, unless there has been less than 10% improvement in the last 6 months in at least one of the measures indicative of iron overload (serum ferritin, LIC, or cardiac MRI T2*), in which case the dose can be increased up to 33 mg/kg t.i.d. for patients who were receiving lower doses. If a patient who is already at that dose level is not showing improvement but has consented to participate in the extension study, he/she must remain at 33 mg/kg t.i.d. since that is the maximum permitted.
- For patients who were treated with deferoxamine in LA38-0411, the initial dose of deferiprone will be 15 mg/kg t.i.d. through Week 1, increasing to 20 mg/kg t.i.d. at Week 2 and then to 25 mg/kg t.i.d. at Week 3. It may be further increased to up to a limit of 33 mg/kg t.i.d. if any of the following is true:
 - \circ Transfusional iron input > 0.3 mg/kg/day in the 3 months prior to Visit 1
 - o Serum ferritin ≥2500 μg/L at Visit 1
 - o LIC \ge 15 mg/g dry weight at Visit 1
 - Cardiac $T2* \le 20$ ms at Visit 1

Since the Visit 1 results for the above parameters may not be immediately available, the dosage beyond Week 3 cannot be confirmed at the time when the first supply of drug is dispensed. Details of how dispensing is to be handled at Visit 1 are provided in Section 5.1.

- For any patient, the dose can be increased up to a limit of 33 mg/kg t.i.d. if any of the following is true:
 - At any time during the trial if mean daily transfusional iron input increases to more than 0.3 mg/kg body weight for at least 3 consecutive months
 - o If in the past 6 months there has been less than 10% improvement in at least one of the measures indicative of iron overload (serum ferritin, LIC, or cardiac MRI T2*)
- For any patient, the dose can be decreased at any time during the trial based on assessment of safety markers for adverse reactions that are possibly dose dependent (e.g., gastrointestinal upset, increases in serum liver enzyme levels, and arthropathies).

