5 STUDY PROCEDURES

The procedures and assessments to be conducted at each study visit are shown in Table 5.1.

 Table 5.1
 Table of study procedures

Procedure	Visit 1	Blood Draws ²	Visit 2	Visit 3	Visit 4	Visit 5	Visit 6	Visit 7	Visit 8	Visit 9 or Early Termination
Week:	0		13	26	39	52	65	78	91	104
Informed consent/assent	X									
Eligibility criteria	X									
Prior and concomitant medications	X		X	X	X	X	X	X	X	X
Transfusion information (if applicable) ³	X	X	X	X	X	X	X	X	X	X
Serum pregnancy testing (if applicable) ⁴	X		X	X	X	X	X	X	X	X
Physical examination	X					X				X
Vital signs (including weight and height) 5	X		X	X	X	X	X	X	X	X
12-lead ECG	X					X				X
Contraceptive counseling	X		X	X	X	X	X	X	X	X
Serology	X									X
Hematology	X	X	X	X	X	X	X	X	X	X
Biochemistry ⁶	X			X		X		X		X
Serum ferritin	X		X	X	X	X	X	X	X	X
Urinalysis	X					X				X
Liver MRI	X					X				X
Cardiac MRI T2*	X					X				X

CONFIDENTIAL Page 25 of 69

Procedure	Visit 1	Blood Draws ²	Visit 2	Visit 3	Visit 4	Visit 5	Visit 6	Visit 7	Visit 8	Visit 9 or Early Termination
Week:	0		13	26	39	52	65	78	91	104
Dose calculation/verify and adjust dose level	X		X	X	X	X	X	X	X	
Collect used and unused study medication			X	X	X	X	X	X	X	X
Dispense study medication	X		X	X	X	X	X	X	X	
Dispense patient diary card	X		X	X	X	X	X	X	X	
Review and collect diary card			X	X	X	X	X	X	X	X
Adverse events	X		X	X	X	X	X	X	X	X

Visit 1 of study LA38-EXT is also the final visit of study LA38-0411. It serves as the baseline visit for those patients who received deferoxamine in LA38-0411 and will now be receiving deferiprone for the first time. (For patients who received deferiprone in LA38-0411, the measures obtained at the baseline visit of the LA38-0411 study will be used as the baseline measures for LA38-EXT as well.)

- Record volume of blood that the patient received during the transfusion, and the mean hematocrit of the packed red blood cell units transfused
- ⁵ Females of childbearing potential only
- ⁵ Height will be measured only at Visits 1, 5, and 9
- ⁶ At Visits 1, 3, 5, 7, and 9, the blood sample must be drawn following a 10-hour fast

For Group 1, hematology testing is to be done monthly throughout the study. For Group 2, it is to be done weekly up to Visit 3 (Week 26), biweekly up to Visit 5 (Week 52), and monthly thereafter. At the quarterly site visits, this testing will be done as part of the routine procedures, and at the other time points it can be done at a local laboratory instead of at the site.

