7 MEASUREMENTS AND EVALUATIONS

7.1 Efficacy Measurements

7.1.1 Liver Iron Concentration

The liver contains 70% or more of total body iron, (17) justifying the use of liver iron concentration (LIC) as a measure of body iron load. (18,19,20,21) In the absence of effective iron chelation therapy, transfusion-dependent patients experience a progressive increase in LIC. (22) Although liver iron concentrations may differ from the concentrations of iron in other organs, it has been reported that patients with LIC greater than 7 mg iron/g liver (dry weight; dw) are at increased risk of iron-induced toxicity such as cardiac disease, hepatic fibrosis, diabetes mellitus and death. (19,23,24) The current goal for chelation therapy in transfusion-dependent patients is to maintain an "optimal" body iron burden corresponding to hepatic storage concentrations of less than 7 mg/g dw. (19)

MRI scans for liver iron will be performed at Visit 1, Visit 5, and Visit 9 (or early termination), and will be transmitted to a central laboratory for interpretation and LIC calculation.

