9.4.1.3 Analysis of Efficacy

Changes in LIC, in cardiac MRI T2*, and in serum ferritin from baseline to Year 1(both groups; Group 1 data are from LA38-041), from baseline to Year 2 (both groups), and from baseline to Year 3 (Group 1 only) will be summarized with descriptive statistics, and will be tested against no change using a one-sample t-test. The changes in these 3 efficacy measures from the start of deferiprone therapy to the last visit of LA38-EXT in all patients, irrespective of whether deferiprone therapy was initiated in LA38-0411 or in LA38-EXT, will also be tested using a one-sample t-test. In addition, the percentages of responders will be tabulated for Year 1 (both groups; Group 1 data are from LA38-0411), for Year 2 (both groups), and for Year 3 (Group 1 only) of deferiprone therapy.

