2.2 Secondary Objective

To evaluate the efficacy of deferiprone in the treatment of iron overload in patients with sickle cell disease or other anemias who have received deferiprone for up to 3 years.

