6.3.3 Analysis of Efficacy

Changes in LIC, in cardiac MRI T2*, and in serum ferritin from baseline to Year 1 (both groups; Group 1 data are from LA38-0411), from baseline to Year 2 (both groups), and from

baseline to Year 3 (Group 1 only) will be summarized with descriptive statistics and will be tested against no change using a one-sample t-test. The changes in these 3 efficacy measures from the start of deferiprone therapy to the last visit of LA38-EXT in all patients, irrespective of whether deferiprone therapy was initiated in LA38-0411 or in LA38-EXT, will also be tested using a one-sample t-test. In addition, the percentages of responders will be tabulated for Year 1 (both groups; Group 1 data are from LA38-0411), for Year 2 (both groups), and for Year 3 (Group 1 only) of deferiprone therapy. The change from baseline to end of LA38-041 for deferoxamine and the change from baseline to end of LA38-EXT for deferiprone in Group 2 will be compared.

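### The LIC and ferritin analyses take no account of transfusional iron input, and one overall mean cannot show whether input changed between years or between Group 2's two treatments

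*SAP*

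**What the plan says.** The secondary objective is the efficacy of deferiprone in patients "who have received deferiprone for up to 3 years" (SAP 2.2). LA38-EXT is single-arm.

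Under SAP 6.3.3, changes in LIC, cardiac T2* and serum ferritin at each year "will be tested against no change using a one-sample t-test". The same test is applied to the change "from the start of deferiprone therapy to the last visit of LA38-EXT in all patients". Protocol 9.4.1.3 gives the same method. Responders are counted at a fixed 20% threshold. SAP 6.1.2 adds a comparison within Group 2: the change on deferoxamine in the parent study against the change on deferiprone in the extension. It is meant to judge whether deferiprone maintains or improves LIC and T2* after the switch, and Tables 14.2.1.4 and 14.2.2.4 report it with a t-test.

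Transfusions are recorded throughout, and iron input is calculated for each one (Protocol 5.1). Input also enters the dosing rules: Protocol 3.3 lists as one ground for an increase "At any time during the trial if mean daily transfusional iron input increases to more than 0.3 mg/kg body weight for at least 3 consecutive", counted in months. In the analysis, the only summary of input is "Table 14.5.1 Overall mean of transfusional iron input (mg/kg/day) during the study – Safety population". Its shell has one row, one mean per group and a between-group t-test. Otherwise the transfusion data appear only in listings.

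**The concern.** The protocol treats transfusional input as a driver of the endpoints. Section 7.1.1 says that "In the absence of effective iron chelation therapy, transfusion-dependent patients experience a progressive increase in LIC", and Section 7.1.3 attributes rising ferritin to continuing transfusional input. An observed change is therefore the balance of input and removal, and only removal is the drug's effect. With no concurrent control, nothing in the design absorbs a change in transfusion practice over two or three years. The extension's inclusion and withdrawal criteria (Protocol 4.2, 4.5) do not require transfusion to continue at any given rate.

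Four results depend on this: the size of the LIC and ferritin changes, the responder percentages, the comparison of Years 1, 2 and 3, and the Group 2 comparison of deferoxamine with deferiprone. The last is the most exposed. It compares two drugs across two calendar periods in the same patients, and no table shows whether input was the same in both.

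**Working it through.** **1. Where iron input is used**

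| Place | Use of input |
|---|---|
| Protocol 3.3 | One ground for a dose increase |
| Protocol 5.1 | Calculated per transfusion |
| SAP 6.3.3, change tests | None |
| SAP 6.3.3, responders | None |
| SAP 6.3.3, Group 2 comparison | None |
| SAP Table 14.5.1 | One overall mean per group |

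The period covered by Table 14.5.1 is not defined. Group 1's Year 1 lies in LA38-0411, so its mean could cover two years or three. In either case one number cannot show a trend or separate Group 2's two treatment periods.

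**2. Balance.** Let I be input and R removal, both in mg/kg/day, and m the dry liver mass in g per kg body weight. Then

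change in LIC per year = (I − R) × 365 × 0.70 / m.

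The 0.70 is the liver share in Protocol 7.1.1, which says 70% or more; applying it to iron gained or lost is an assumption. The documents do not give m. Taking the liver as 2 to 2.5% of body weight with a dry fraction of 0.2 to 0.3 gives m from 1000 × 0.02 × 0.2 = 4 to 1000 × 0.025 × 0.3 = 7.5.

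Two results follow. If I is positive and R is zero, LIC cannot fall. If R is unchanged, a difference in I passes straight into the change in LIC.

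**3. Size, with R unchanged**

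- 0.1 mg/kg/day: 0.1 × 365 × 0.70 = 25.55 mg/kg per year; 25.55/7.5 = 3.4 and 25.55/4 = 6.4 mg/g dry weight per year.
- 0.05 mg/kg/day: half of that, 1.7 to 3.2 mg/g per year.

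**4. Against the responder threshold.** A 20% fall is 0.20 × 7 = 1.4 mg/g at a baseline of 7 mg/g (the level in Protocol 7.1.1) and 0.20 × 15 = 3.0 mg/g at 15 mg/g (the level in Protocol 3.3). The input difference worth that much in one year is threshold × m / 255.5, since 365 × 0.70 = 255.5:

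- Baseline 7: 1.4 × 4/255.5 = 0.02 to 1.4 × 7.5/255.5 = 0.04 mg/kg/day.
- Baseline 15: 3.0 × 4/255.5 = 0.05 to 3.0 × 7.5/255.5 = 0.09 mg/kg/day.

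These are well below the 0.3 mg/kg/day in the dosing rules.

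**5. Sensitivity of the planned test.** The documents give no alpha, SD or power, so there is no figure to reproduce. The parent study plans 300 patients at 2:1, so at most about 200 reach Group 1 and 100 reach Group 2. Assuming a two-sided 5% level, a mean shift of 0.2 SD from any source gives noncentrality 0.2 × √100 = 2.0 or 0.2 × √200 = 2.83, and the one-sample t-test rejects 51% or 80% of the time.

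In a 4,000-run simulation the whole shift (0.2 or 0.3 SD) came from changed input, with an assumed correlation of 0.5 between change in input and outcome. The regression intercept at unchanged input was rejected in 4.7% to 5.5% of runs. Adjustment therefore removes the shift when the linear model is right.

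**The case against.** A reader might go further and infer that a fall caused by fewer transfusions would be credited to deferiprone, so that the analysis scores efficacy in reverse. The documents do not support that. Protocol 7.1.3 says there is no natural route for excreting excess iron. On that statement, fewer transfusions slow accumulation but do not lower the load, and a net fall needs removal. Exchange transfusion is a possible exception, because blood is also taken out. With ongoing simple transfusion at steady input, zero change is already a demanding null. The rejection rates in step 5 are therefore not false-positive rates for drug activity: if removal balanced the earlier input, the drug was working. They show only how readily a shift in the mean moves the test.

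Other objections also stand in part:

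- Nothing shows that mean input drifted. Entrants come from a trial of anemias requiring regular transfusion (Protocol 1.2). The Table 5.1 row beginning "Transfusion information (if applicable" means only that details are recorded when a transfusion takes place. The 0.3 mg/kg/day rule concerns individual patients.
- The upper end of the illustration may be too high. Protocol 1.1.1 cites a mean liver iron of 13.68 mg/g after a mean 57 months of transfusion. If accumulation was linear from near zero, that is 13.68 × 12/57 = 2.9 mg/g per year, less than the 3.2 given for a difference of 0.05 mg/kg/day. Chelation status is not stated there, so the check is rough.
- Input is measured after baseline and can lead to a dose change, so adjusting for it does not isolate a drug effect cleanly.
- Efficacy is secondary, the randomized comparison with deferoxamine lies in LA38-0411, and the protocol synopsis allows additional analyses.

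None of this makes the four results in question interpretable when input changes. A listing of transfusions does not replace a planned summary.

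**Conclusion.** The gap is real and of moderate weight. No efficacy analysis uses iron input, and Table 14.5.1 cannot show whether it changed. The consequence concerns size and comparison: changed input can move the LIC and ferritin changes, the responder rates, the year-to-year pattern and the Group 2 comparison up or down, and stable LIC under heavy input earns no credit. It does not follow that an observed fall would be spurious.

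The scale, about 3.4 to 6.4 mg/g per year for each 0.1 mg/kg/day, rests on the protocol's 70% share, an assumed dry liver mass and unchanged removal. The actual shift cannot be computed from the documents. Since this is a secondary objective, the change is one the sponsor should make rather than one on which the study depends.

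**What to change.** Keep the planned t-tests. Before database lock:

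1. **Table 14.5.1.** Define the period covered. Report mean input by group for each yearly interval (LA38-0411 year, extension Year 1, extension Year 2) and each treatment period, in the efficacy population as well as the Safety population. Subtract blood removed at exchange where it was recorded, and state where it was not. The removed volume and hematocrit are specified only under the regular blood draws in Protocol 5.1, so net input may be incomplete.
2. **SAP 6.3.3.** Add one supportive model of LIC change, and likewise of ferritin change, on baseline value and mean iron input over the same interval, reporting the estimated change at a reference input fixed in advance.
3. **Group 2 comparison.** Analyse it within patient and include the difference in input between the two periods. The deferoxamine period is one year and the deferiprone period up to two, so express both per year.
4. **Optional.** Tabulate change and responders by input at or below versus above 0.3 mg/kg/day, the one cut the protocol supplies, with mean dose beside each stratum.

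The cost is SAP wording and a few tables from data the protocol already requires, with no new visits or procedures. Because input is post-baseline and linked to dose, these analyses must be labelled supportive, and some strata will be small.
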